8.1 General Principles

The objective of the data screening is to assess the quantity, quality, and statistical characteristics of the data relative to the requirements of the planned analyses.

The database will be subjected to edit checks outlined in the data validation specifications plan by Amgen Clinical Data Management (CDM) department. Any outstanding data issues will be communicated to CDM for resolution before the database is locked.

8.2 Data Handling and Electronic Transfer of Data

The Amgen Global Study Operations-Data Management (GSO-DM) department will provide all data to be used in the planned analyses. This study will use the RAVE database.

8.3 Handling of Missing and Incomplete Data

Rule for handling missing data related to endpoints are described in the endpoint definitions ([section 6](#)) or in the description of analyses ([section 10](#)). The handling of incomplete and partial dates for adverse events and concomitant medications are described in [Appendix B](#).

8.4 Detection of Bias

Methods to detect bias are described in the analyses of particular endpoints

8.5 Outliers

Any suspected outliers will be investigated by the study team and will be included in the database unless determined to be an error or there is supporting evidence or explanation to justify the exclusion. Any outliers excluded from the analysis will be discussed in the Clinical Study Report (CSR), including the reasons for exclusion and the impact of their exclusion on the study.

8.6 Distributional Characteristics

Not Applicable

8.7 Validation of Statistical Analyses

Programs will be developed and maintained, and output will be verified in accordance with current risk-based quality control procedures.

Tables, figures, and listings will be produced with validated standard macro programs where standard macros can produce the specified outputs.

The production environment for statistical analyses consists of Amgen-supported versions of statistical analysis software; for example, the SAS System version 9.4 or later.

9. Statistical Methods of Analysis

9.1 General Considerations

Continuous variables will be summarized by the non-missing sample size (n), mean, standard deviation, median, first and third quartiles, minimum, and maximum.

Categorical variables will be summarized by the n and percentage in each category.

Point estimates for binomial proportions (eg., the primary efficacy endpoint) will be accompanied by 2-sided exact binomial 95% confidence intervals

([Clopper and Pearson, 1934](#)). Time to event endpoints will be summarized with Kaplan-Meier (KM) curves, KM proportions at selected time points, KM quartiles (when estimable), the number of subjects with events, the number of subjects censored, and the pattern of censoring. Point estimates of KM quartiles

([Brookmeyer and Crowley, 1982](#)) and KM proportions ([Kalbfleisch and Prentice, 1980](#)) will be accompanied by 2-sided 95% confidence intervals.

9.2 Subject Accountability

The disposition of all enrolled subjects will be tabulated. Number of subjects screened, enrolled, received blinatumomab along with the reasons for discontinuing blinatumomab and discontinuing study will be summarized. The number of subjects who completed and discontinued from the run-in period, and their reasons for discontinuation will also be summarized.

Key study dates for the first and last subject enrolled, first and last subject's blinatumomab start date, last subject's blinatumomab end date and last subject's end of study date will be presented.

9.3 Important Protocol Deviations

Important Protocol Deviations (IPDs) categories are defined by the study team before the first subject's initial visit and updated during the IPD reviews throughout the study

prior to database lock. These definitions of IPD categories, subcategory codes, and descriptions will be used during the course of the study. Eligibility deviations are defined in the protocol.

9.4 Demographic and Baseline Characteristics

The following demographic and baseline disease characteristics will be summarized using descriptive statistics for the Pre-Treatment Analysis Set and the Primary/Full Analysis Set. If multiple races have been reported for a subject, the subject will be categorized as multiple race as well as by combination of races.

The baseline characteristics to be summarized include:

- Age at enrollment (summary statistics and age categories <65, 65-74, 75-84, ≥ 85 years)
- Race (American Indian or Alaska Native, Asian, Black or African American, Native Hawaiian or Pacific Islander, White, Other)
- Geographical region (North America, Europe, rest of world)
- Disease Stage (Ann-Arbor-Staging) at diagnosis (I, IE, II, IIE, II bulky, III, IV)
- International prognosis index(IPI) at diagnosis and secondary IPI at relapse (Low (0-1), Low – intermediate (2), High – intermediate (3), High (4-5))
- Age-adjusted IPI (aalPI) at diagnosis and secondary aalPI at relapse (Low (0), Low - intermediate (1), High – intermediate (2), High (3))
- Extranodal disease: (Yes, No)
- Cell of Origin Determination (GCB, Non-GCB, ABC, Not done)
- Bcl-2 rearrangement (Positive, Negative, Indeterminate)
- Bcl-6 rearrangement (Positive, Negative, Indeterminate)
- C-myc rearrangement (Positive, Negative, Indeterminate)
- Bcl-2 overexpression (Positive, Negative, Indeterminate)
- Bcl-6 overexpression (Positive, Negative, Indeterminate)
- C-myc overexpression (Positive, Negative, Indeterminate)
- Double-hit (Yes, No, Not Done)
- Double protein expression (Yes, No, Not Done)
- Triple-hit (Yes, No)
- Refractory to frontline treatment (Yes, No)
- Relapse within 1 year of diagnosis (Yes, No)
- High-risk first complete remission (Yes, No)

9.5 Efficacy Analyses

Table 9-1. Primary Efficacy Endpoint Summary Table

Endpoint	Primary Summary and Analysis Method	Sensitivity Analysis
Proportion of subjects who achieve MRD response (MRD negativity) after cycle 1 of blinatumomab. MRD negativity is determined as the best MRD response on day 57 or day 71(+3 days) via MRD testing.	The MRD-negative rate at the end of cycle 1 of blinatumomab is calculated as the number of subjects with MRD-negative status after treatment with blinatumomab divided by the total number of subjects in the Primary Analysis Set for Primary Analysis. Exact binomial 95% CI will be summarized. The Full Analysis Set will be used at final analysis..	A sensitivity analysis will be performed using the Target Dose Analysis Set for the final analysis.

Table 9-2. Secondary Efficacy Endpoint Summary Table

Endpoint	Primary Summary and Analysis Method	Sensitivity Analysis
PFS	Kaplan-Meier (KM) analyses (KM plot and KM estimates) on the Full Analysis Set.	A sensitivity analysis will be performed using the Target Dose Analysis Set for the final analysis
Duration of MRD-negative status	Kaplan-Meier (KM) analyses (KM plot and KM estimates) on the Full Analysis Set.	A sensitivity analysis will be performed using the Target Dose Analysis Set for the final analysis
OS	Kaplan-Meier (KM) analyses (KM plot and KM estimates) on the Full Analysis Set.	A sensitivity analysis will be performed using the Target Dose Analysis Set for the final analysis.

Secondary efficacy endpoints will be assessed only at final analysis.

Table 9-3. Exploratory Efficacy Endpoint Summary Table

Endpoint	Primary Summary and Analysis Method	Sensitivity Analysis
MRD-negative rate	The MRD-negative rate will be summarized at each time point measured following blinatumomab treatment using both Primary and Full Analysis Sets.	A sensitivity analysis will be performed using the Target Dose Analysis Set for the final analysis
Incidence of alloHsCT	Incidence of alloHsCT (number of subjects with alloHsCT), including the methodology (Intensity of Conditioning Regimen and Donor Type) and clinical outcomes (Maximum grade of aGVHD) will be summarized using Full Analysis Set.	A sensitivity analysis will be performed using the Target Dose Analysis Set for the final analysis
To describe the relationship between clinical outcomes and baseline covariates and response to blinatumomab treatment	MRD negative rates in subgroups specified in section 4.2 will be presented using Primary and Full Analysis Sets	A sensitivity analysis will be performed using the Target Dose Analysis Set for the final analysis
To describe MRD status relative to clinical relapse	KM analysis of PFS and OS stratified by MRD response status after cycle 1 (landmark analysis on Day 75) will be performed in both Primary and Full Analysis Sets	A sensitivity analysis will be performed using the Target Dose Analysis Set for the final analysis
The percentage of MRD positivity in PET-CT negative subjects post aHsCT	Summary of subject who had PET-CT negative status post aHsCT and become MRD positivity status during run in period will be presented with pretreatment analysis set.	A sensitivity analysis will be performed using the Target Dose Analysis Set for the final analysis
Rate and timing of MRD negative to MRD positive change during the 24-month run-in period	Summary of MRD Status in different time points will be presented during run in period with pretreatment analysis set.	A sensitivity analysis will be performed using the Target Dose Analysis Set for the final analysis

Exploratory efficacy endpoints will be analyzed at primary analysis by using primary analysis set and pretreatment analysis set, and at final analysis using the Full analysis set.

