10.1.2.3 Target Dose Analysis Set

The target dose analysis set will include all subjects from the full analysis set who completed at least 7 days of infusion on the highest intended dose. In addition, all subjects who discontinue treatment with blinatumomab due to disease progression during cycle 1 will also be included in the target analysis set. The target dose analysis set will be used as sensitivity analysis set for the final analysis.

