10.1.4 Handling of Missing and Incomplete Data

Subjects missing post-baseline MRD assessments will be considered not to have achieved MRD-negative status.

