10.4.2 Primary Efficacy Endpoint

MRD-negative rate at the end of cycle 1 of blinatumomab. MRD is defined as negative when the tumor clone sequence in plasma is below the assay's limit of detection (to be determined in the assay validation).

MRD-negative rate is calculated as the number of subjects with MRD-negative status after treatment with blinatumomab divided by the total number of subjects in the respective analysis set.

Exact binomial 95% CI will be used to analyze MRD-negative rate.

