2.1 Objectives and Endpoints

Objectives	Endpoints
Primary	

 To determine minimal residual disease (MRD) negative rate following blinatumomab treatment in high-risk Diffuse Large B-cell Lymphoma (DLBCL) subjects who are MRD-positive post-autologous hematopoietic stem cell transplantation (aHSCT). 	
 MRD negativity in cycle 1 of blinatumomab, defined as the best MRD response on day 57 or day71(+3 days) via MRD testing
Secondary	

 To describe the efficacy of blinatumomab in relation to progression-free survival (PFS), duration of MRD-negative status, and overall survival (OS) 	
 PFS Duration of MRD negative status OS

 To evaluate the safety and tolerability of blinatumomab 	
 Incidence, grade and severity of treatment emergent adverse events (AE)
Exploratory	

 To describe the incidence of anti-blinatumomab antibody 	
 Incidence of anti-blinatumomab antibody formation

 To describe the MRD-negative rate over time following blinatumomab treatment 	
 MRD negative rate calculated at each time point measured following blinatumomab treatment

 To describe rate, features and outcomes of allogeneic hematopoietic stem cell transplantation (alloHSCT) following treatment with blinatumomab 	
 Incidence of alloHSCT (rate and number of subjects with alloHSCT) and the feature and clinical outcomes

Objectives	Endpoints
Exploratory (Continued)	

 To describe the relationship between clinical and baseline parameters and response to blinatumomab treatment 	
 Relationship between pre-specified co-variables with MRD negative status and clinical outcomes

 To describe MRD status relative to clinical relapse 	
 Relationship between MRD negative status and clinical relapse

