Duration of MRD-negative status will be defined from the time when a negative MRD result is first established until documented MRD-positive reoccurrence, or disease progression (or, death due to any cause). Subjects without any of these events at the time of the analysis will be censored at their last disease assessment date.

End of Treatment

End of Treatment is defined as the last assessment for the protocol-specified treatment phase of the study for an individual subject.

End of follow-up

End of Follow-up is defined as when the last subject completes the last protocol-specified assessment in the study.

End of study

For a subject: End of study for a subject is defined as the last day that protocol-specified procedures are conducted for an individual subject.

For the study as a whole: The end of trial is defined as the date when the last subject is assessed or receives an intervention for evaluation in the study (ie, last subject last visit), following any additional parts in the study (eg, long-term follow-up), as applicable.

The primary completion date: The primary completion date is defined as the date when the last subject is assessed or receives an intervention for the final collection of data for the primary endpoint, for the purposes of conducting the primary analysis, whether the study concluded as planned in the protocol or was terminated early.

High-risk first complete remission

High-risk first complete remission is defined as subjects who an interim PET-CT positive or less than complete remission to frontline chemotherapy AND achieved complete remission to platinum-containing salvage)

as collected on the Prior Anti-Cancer Therapies for Current Malignancies eCRF page.

International prognostic index (IPI)

International prognostic index (IPI) at diagnosis will be collected on the 'IPI at diagnosis' field on the DLBCL Disease History (Staging and Risk Initial) eCRF page. Secondary IPI at relapse will be collected on the 'IPI prior to S1' field on the DLBCL Disease History (Staging and Risk Prior S1) eCRF page.

Minimum residual disease (MRD)

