Minimum residual disease (MRD) is defined as negative when the tumor clone sequence in plasma is below the assay limit of detection (to be determined in the assay validation). Positive MRD status will be defined as plasma levels above the assay limit of detection. All subjects in the treatment period are considered MRD positive, regardless whether the Cycle 1 Day 1 MRD test results are positive or negative because these subjects have been tested MRD positive in the run-in period.

Overall survival (OS)

Overall survival will be defined from the first dose of blinatumomab treatment until death due to any cause. Subjects still alive at the time of the analysis will be censored at date last known to be alive.

Percent of intended dose of blinatumomab

For cycle 1, the percent of intended dose of blinatumomab will be the cumulative dose divided by the planned cumulative dose. The planned cumulative dose for cycle 1 will be $(9 \mu\text{g} \times 7 \text{ days}) + (28 \mu\text{g} \times 7 \text{ days}) + (112 \mu\text{g} \times 42 \text{ days}) = 4963 \mu\text{g}$.

Progression free survival (PFS)

Progression free survival (PFS) is calculated as the time from the date of first dose of blinatumomab until the date of diagnosis of relapse of lymphoma (by PET-CT, CT, clinical assessment or relapse biopsy, whichever is the preferred method), or date of death, whichever is the earliest. Subjects alive who did not have progression will be censored at last date of tumor assessment.

Refractory to frontline treatment

Refractory to frontline treatment is defined as failure to achieve complete response as the best response after completion of frontline chemotherapy, as collected on the Prior Anti-Cancer Therapies for Current Malignancies eCRF page.

Relapse within 1 year of diagnosis

A subject will be classified as relapsed within 1 year of diagnosis if the difference between the earliest date of relapse captured on the History of Relapses eCRF page and date of diagnosis on DLBCL Medical History eCRF page is less than 1 year.

Date of first relapse – Date of diagnosis + 1 < 365.25

Stage at diagnosis

As collected on the 'Ann-Arbor' field on the DLBCL Disease History (Staging and Risk Initial) eCRF page.

Study day 1

Study day 1 is defined as the first day that protocol-specified investigational products are administered to the subject.

Study day

Pre study day 1: study day= (date – date of Study Day 1)

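### A negative plasma sample drawn on or after documented relapse can still make a subject an MRD-negative responder; one scoring sentence in the SAP closes the gap

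*SAP*

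**What the plan says.** **Primary endpoint.** SAP 9.5, Table 9-1: "MRD negativity is determined as the best MRD response on day 57 or day 71(+3 days) via MRD testing". SAP 2.1 has the same rule: "defined as the best MRD response on day 57 or day71(+3 days) via MRD testing". The status itself is purely molecular. Protocol 10.4.2 says "MRD is defined as negative when the tumor clone sequence in plasma is below the assay's limit of detection", and SAP Section 5 agrees. On the rate, protocol 10.4.2 says "MRD-negative rate is calculated as the number of subjects with MRD-negative status after treatment with blinatumomab divided by the total number of subjects" in the analysis set, and SAP 9.5.1 repeats this.

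**Forced non-response.** The only such rule is in protocol 10.1.4: "Subjects missing post-baseline MRD assessments will be considered not to have achieved MRD-negative status". SAP Section 5 restates it under the duration definition.

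**Duration of MRD-negative status.** SAP Section 5 runs it from the first negative result "until documented MRD-positive reoccurrence, or disease progression (or, death due to any cause".

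**Imaging in cycle 1.** Under protocol 3.1 and Table 4 (footnote g), the PET-CT at day 71 (+3) is done only if the subject is still MRD-positive on day 57 or has clinical signs of progression. An MRD sample is due at the same visit. Neither document links the scan result to the primary endpoint.

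**Sampling after treatment stops.** Protocol 6.2.1.3 stops blinatumomab at progression and mentions continued response assessment only for adverse-event stops. Protocol 8.1 and 12.4 nevertheless keep the assessment schedule open for subjects who are off treatment.

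**The concern.** The trial treats subjects in remission on PET-CT whose residual disease is visible only in plasma, and asks whether the drug clears it. A subject with documented lymphoma relapse no longer has minimal residual disease, whatever the plasma assay shows at that moment. A scoring rule that looks only at plasma can count such a subject as a success. The error has one direction: excluding post-relapse samples can lower the MRD-negative count or leave it alone, but never raise it.

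The planned outputs at the primary analysis would also not show it clearly. Secondary endpoints, including PFS, wait for the final analysis (SAP 9.5). The landmark analysis in SAP 9.5.3 keeps only subjects still followed for PFS or OS at day 75, so earlier relapses drop out of its PFS part. Disease-related events are tabulated by organ class, not by MRD response (SAP Table 9-4).

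**Working it through.** **Step 1: can the case arise under the rules as written?** Take a subject who is MRD-positive on day 57.

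- Table 4 then calls for PET-CT at day 71 (+3), and an MRD sample is due at that visit.
- Suppose the scan shows relapse on day 71 and the sample, drawn the same day, is below the detection limit.
- Best of day 57 (positive) and day 71 (negative) is negative, so the subject is a responder under Table 9-1.
- If that is the first negative sample, duration runs from day 71 to relapse on day 71: 71 − 71 = 0 days.
- If the sample is drawn on day 74, within the window, duration is 71 − 74 = −3 days.

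The dates are illustrative. A subject who stops for progression before day 57 but is still sampled gives the same result. No rule in either document prevents it.

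**Step 2: reproduce the plan's own intervals.** Inputs: N = 30 (SAP 6.2); two-sided exact 95% limits (SAP 9.1); 10% benchmark (SAP 2.2). For x responders of n, the lower limit is the 0.025 quantile of Beta(x, n − x + 1) and the upper limit is the 0.975 quantile of Beta(x + 1, n − x). For 8, 9, 11, 12 and 14 of 30 this gives 12.3–45.9, 14.7–49.4, 19.9–56.1, 22.7–59.4 and 28.3–65.7%. All five match SAP Table 3-1 and protocol 10.2.

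**Step 3: remove k post-relapse responders.** The documents give no rate, so k is an assumption, shown over a range. Each subject is worth 1/30 = 3.3 points.

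| Scored as responders | k removed | Remaining | Exact 95% CI (%) | Lower limit above 10%? |
|---|---|---|---|---|
| 8 | 0 | 8/30 (26.7%) | 12.3–45.9 | yes |
| 8 | 1 | 7/30 (23.3%) | 9.9–42.3 | no |
| 9 | 1 | 8/30 (26.7%) | 12.3–45.9 | yes |
| 9 | 2 | 7/30 (23.3%) | 9.9–42.3 | no |
| 11 | 3 | 8/30 (26.7%) | 12.3–45.9 | yes |

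The smallest count with a lower limit above 10% is 8/30 (12.28%); 7/30 gives 9.93%.

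**Step 4: how often would a single subject matter to the benchmark?** Only at exactly 8/30. If the true rate is 30%, P(at least 8) = 0.719 and P(at least 9) = 0.568, so P(exactly 8) = 0.719 − 0.568, about 0.15. One misclassified subject would also have to be among those 8.

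**The case against.** The strongest reply is that the endpoint is meant to be molecular. The objective is an MRD-negative rate, plasma below the detection limit is MRD-negative by definition, and clinical relapse has its own endpoints. This stands in part and sets the limits of the point.

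- **Negative on day 57, relapse by day 71.** A reader might infer that this subject is also wrongly scored. The documents do not support that. The subject met the stated endpoint before relapsing, and the duration definition treats progression as the end of a response, not its erasure. With a first negative on day 57 and relapse on day 71, duration is 71 − 57 = 14 days. Reclassifying these subjects would change what is being estimated and would remove the shortest durations from the duration endpoint.
- **Target Dose Analysis Set.** Protocol 10.1.2.3 says "all subjects who discontinue treatment with blinatumomab due to disease progression during cycle 1 will also be included in the target analysis set". A reader might take this to mean that progression counts as failure. It settles only who is in the denominator and says nothing about response status.
- **Few subjects will be affected.** This stands. An early progressor may have no day 57 or day 71 sample and so default to non-response. But that depends on whether blood was drawn, not on a rule about relapse.
- **No decision hangs on 10%.** This also stands. SAP 2.2 says that no formal hypothesis is tested.

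**Conclusion.** The gap is real and narrow. The primary endpoint has no condition that the subject is relapse-free when the qualifying sample is drawn, so an overtly relapsed subject can be counted as a responder, with a duration that makes no sense if that sample is the first negative one. I class it as a cheap improvement.

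Its size is 3.3 points per subject, always upward. The lower limit crosses 10% through one subject only if exactly 8/30 were scored as responders. The number of such subjects cannot be estimated from the documents.

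A reader might try to estimate it from the surveillance figures in protocol 2.2. The 88.2% and 97.8% predictive values fit 15/17 and 88/90, which implies 2 of 17 progressions missed in plasma. A 3.5-month median lead time, taken as exponential with no drug effect, gives 1 − 0.5^(74/106.5) = 38.2% relapsed by day 74, and 30 × 0.382 × 2/17 is about 1.35 subjects. That figure does not carry over:

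- The cohort was not selected for detectable DNA, whereas every treated subject here has already tested plasma-positive.
- The lead time is a median among relapsers, counted from detection and not from first dose.
- Applying it to all 30 ignores the positive predictive value.
- It assumes that the drug does nothing.

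The honest statement is that the frequency is unknown and probably low.

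**What to change.** Add to SAP 2.1, Table 9-1 and 9.5.1, and to the duration definition in SAP Section 5: an MRD sample collected on or after relapse documented by any method in the PFS definition cannot qualify as MRD-negative, either for the primary endpoint or for the start of MRD-negative duration. Such a subject counts as not MRD-negative unless an earlier day 57 sample, taken before relapse, was negative.

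Add a listing at the primary analysis of every subject with relapse up to the day 71 (+3) assessment, with relapse date and method and all MRD dates and results. This also shows cases where the sample came a day or two before the scan.

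Add one sensitivity analysis that counts day 57 negatives who relapse by the day 71 (+3) assessment as failures. Keep this out of the primary rule.

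Record the clarification in SAP Section 10, which now reports no changes.

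Cost: a few lines in the SAP and one listing, using relapse dates already collected for PFS. The rate may be slightly less favourable. A centrally assayed endpoint also gains a small dependence on locally assessed relapse in an open-label trial, where cycle 1 imaging is done only for day 57 positivity or symptoms. The change concerns scoring only and does not touch clinical management.

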- 209 Subject has known hypersensitivity to immunoglobulins or any of the products or components to be administered during dosing.
- 210 History or evidence of any other clinically significant disorder, condition or disease (with the exception of those outlined above) that, in the opinion of the investigator or Amgen physician, if consulted, would pose a risk to subject safety or interfere with the study evaluation, procedures or completion.
- 211 Women who are pregnant or breastfeeding or planning to become pregnant or breastfeed while receiving blinatumomab and for an additional 48 hours after the last treatment dose of blinatumomab. (Females of child bearing potential should only be included after a negative highly sensitive urine or serum pregnancy test.)
- 212 Women of childbearing potential unwilling to use an acceptable method of effective contraception while receiving blinatumomab and for an additional 48 hours after last dose of blinatumomab.

Note: The pregnancy, breastfeeding and contraceptive requirements are specific to blinatumomab. The investigator is responsible for providing the subject (male and female) with pregnancy and breastfeeding (female only) avoidance requirements for other medications given during the study.

- 213 Currently receiving treatment in another investigational device or drug study or less than 30 days since ending treatment on another investigational device or drug study. Other investigational procedures while participating in this study are excluded.

4.2 Inclusion and Exclusion Criteria – Part 2

4.2.1 Inclusion Criteria – Part 2

- 112 MRD-positive assessment (by NGS analysis) at enrollment or at any time during the run-in 1 period
- 113 PET-CT negative (defined by Deauville criteria ≤ 3) at run-in 2 performed ≤ 3 weeks from **MRD test result available to the site at run-in 1**. Historical PET-CT are allowed if performed ≤ 6 weeks from day 1 (first dose of blinatumomab) and subject has no clinical signs or symptoms suggestive of disease progression (eg, increase in lactate dehydrogenase [LDH] not otherwise explained)

114 Adequate organ function determined ≤ 7 days prior to treatment assignment with blinatumomab as follows:

Hematological:

- ANC $\geq 1.0 \times 10^9/L$
- Hemoglobin ≥ 8 g/L
- Platelet count $\geq 75 \times 10^9/L$

Renal:

- Creatinine clearance ≥ 50 mL/min Cockcroft-Gault equation

Hepatic:

- AST and ALT $< 3 \times$ ULN

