6.1 Full Analysis Set

The full analysis set will include all subjects who received blinatumomab. Subjects who were treated beyond the required sample size of 30 subjects will be included in this analysis set. The full analysis set will be used for the final analysis.

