6.3 Target Dose Analysis Set

The target dose analysis set will include all subjects from the full analysis set who completed at least 7 days of infusion on the highest intended dose. In addition, all subjects who discontinue treatment with blinatumomab due to disease progression during cycle 1 will also be included in the target analysis set. The target dose analysis set will be used as sensitivity analysis set for the final analysis.

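### The Target Dose Analysis Set holds only treated, MRD-positive subjects, so it cannot serve as a sensitivity set for the run-in MRD endpoints, and the final-analysis denominator for those endpoints is contradictory

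*SAP*

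**What the plan says.** The last two rows of SAP Table 9-3 concern MRD before any blinatumomab is given. For the percentage positive after transplant, the main analysis covers subjects who were PET-CT negative and "become MRD positivity status during run in period will be presented with pretreatment analysis set". For change from negative to positive, the entry reads "Summary of MRD Status in different time points will be presented during run in period with pretreatment analysis set". The sensitivity cell of each row then says "A sensitivity analysis will be performed using the Target Dose Analysis Set for the final analysis".

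The definitions that decide who is in that set are:

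- **SAP 6.1:** "The full analysis set will include all subjects who received blinatumomab".
- **SAP 6.3:** the Target Dose Analysis Set takes "all subjects from the full analysis set who completed at least 7 days of infusion on the highest intended dose", and adds that "all subjects who discontinue treatment with blinatumomab due to disease progression during cycle 1 will also be included in the target analysis set".
- **Protocol 4.2.1, criterion 112:** assignment to treatment requires an "MRD-positive assessment (by NGS analysis) at enrollment or at any time during the run-in 1 period".
- **SAP 6.4:** the Pre-treatment Analysis Set is everyone enrolled.

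The MRD definition in SAP Section 5 counts every subject in the treatment period as MRD-positive, on the ground of an earlier positive test in run-in.

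On the final analysis the documents differ. SAP 9.5.3 summarizes the pre-treatment MRD characteristics in the Pre-treatment Analysis Set and does not limit this to the primary analysis. The sentence under Table 9-3 assigns exploratory efficacy endpoints at the final analysis to the Full Analysis Set. SAP 7.4 lists MRD before treatment among the updated estimates, describes those estimates as covering subjects with at least one dose, and names the Full Analysis Set. Protocol 10.3.4 carries the same one-dose description.

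**The concern.** A sensitivity analysis should estimate the same quantity under a different but defensible choice. Here the alternative set is formed by conditioning on the outcome. It leaves out everyone who stayed MRD-negative. It also leaves out subjects who turned positive but failed Part 2 eligibility and so ended the study (Protocol 5 and 7.2.3). The number of days at the highest dose, which is settled after treatment starts, has no bearing on a rate observed before treatment.

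If the cells are followed as written, the report will show a 100% figure labelled as a sensitivity result beside an estimate expected to be near one third. If the sentence under Table 9-3 and SAP 7.4 are followed, the main estimate itself could move from all enrolled subjects at the primary analysis (Protocol 10.3.3) to treated subjects at the final analysis. That would be an unexplained change of denominator. It would come when run-in data may be more complete, because SAP 3.2 allows subjects to turn positive and be treated after the first 30.

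**Working it through.** **Step 1. Membership.** Target Dose Analysis Set ⊂ Full Analysis Set (SAP 6.1, 6.3) ⊂ subjects with an MRD-positive result at enrollment or in run-in (Protocol criterion 112; SAP Section 5). The subjects added for progression in cycle 1 were also treated, so they do not change this. No member can have been MRD-negative throughout, eligibility deviations aside.

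**Step 2. The plan's own figures.** SAP 3.2 plans about N = 90 enrolled and about m = 30 MRD-positive at enrollment or in run-in. The documents state no other expected result for the run-in rows. As a check on the interval method, the Clopper-Pearson formula reproduces all five rows of Table 3-1, for example 9/30: 14.7% to 49.4%.

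**Step 3. Ever MRD-positive by the end of run-in.**

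- Pre-treatment Analysis Set: m/N = 30/90 = 33.3% (exact 95% CI 23.7% to 44.1%).
- Target Dose Analysis Set of size n: n/n = 100% for every n. The exact lower limit is 0.025^(1/n), which is 78.2% for n = 15, 83.2% for n = 20, 86.3% for n = 25 and 88.4% for n = 30. The interval reflects only the size of the set.

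**Step 4. The other quantities in the two rows.** Let k be the number already positive at enrollment. The documents do not give k, so it is varied over its full range, 0 to 30. For simplicity all 30 positive subjects are taken to be treated and to enter the Target Dose Analysis Set (n = 30), and run-in dropout is ignored.

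- Positive at screening: k/90 (Pre-treatment), k/30 (Target Dose).
- Conversion among those negative at screening: (30 − k)/(90 − k) (Pre-treatment), (30 − k)/(30 − k) (Target Dose).

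| k (assumed) | Pre-treatment: positive at screening | Pre-treatment: conversion | Target Dose: positive at screening | Target Dose: conversion |
|---|---|---|---|---|
| 0 | 0/90 = 0% | 30/90 = 33.3% | 0/30 = 0% | 30/30 = 100% |
| 10 | 10/90 = 11.1% | 20/80 = 25.0% | 10/30 = 33.3% | 20/20 = 100% |
| 20 | 20/90 = 22.2% | 10/70 = 14.3% | 20/30 = 66.7% | 10/10 = 100% |
| 30 | 30/90 = 33.3% | 0/60 = 0% | 30/30 = 100% | undefined |

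Conversion in the Target Dose Analysis Set is fixed at 100% wherever it is defined. Positivity at screening is not fixed, but under these assumptions it is 90/30 = 3 times the Pre-treatment figure for every k above 0, purely because the never-positive subjects have been removed. Status by visit and time to positivity also vary with the data, but they are conditional on having become positive and been treated.

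**Step 5. Which set at the final analysis?**

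| Place | Set for run-in MRD endpoints |
|---|---|
| Protocol 10.3.3 (primary analysis) | Pre-treatment |
| SAP Table 9-3, main-method cells | Pre-treatment |
| SAP 9.5.3 | Pre-treatment, no time limit stated |
| SAP, sentence under Table 9-3 (final analysis) | Full Analysis Set |
| SAP 7.4 (final analysis) | Dosed subjects; Full Analysis Set |
| Protocol 10.3.4 (final analysis) | Dosed subjects |

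The last three rows cannot all be followed together with SAP 9.5.3.

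**The case against.** The strongest reply is that this is generic text repeated down a sensitivity column. The same sentence is attached to the MRD-negative rate, PFS and OS, where the Target Dose Analysis Set is a sensible choice. The correct main set is already named in both rows and again in SAP 9.5.3. The endpoints are exploratory, no formal hypothesis is tested, and no decision depends on these cells. It can also be argued that the one-dose wording in SAP 7.4 and Protocol 10.3.4 was meant to bring in subjects treated after the first 30, not to shut out untreated subjects from a run-in summary.

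Most of this stands as a statement about importance. It does not rescue the cells: followed literally, they call for an analysis that cannot inform the estimate it is set beside. The probable intent behind SAP 7.4 is also not what it says, since it names MRD before treatment and the Full Analysis Set together.

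Two stronger readings should be resisted. A reader might infer that everything in these rows would come out at 100%. It would not: SAP 9.5.3 words the first endpoint as MRD status at screening, which is k/n and could lie anywhere from 0% to 100%, and status by visit and timing also vary. A reader might also infer that the set contains only converters. It does not: criterion 112 admits subjects already positive at enrollment, so with an assumed k = 10 converters are 20/30 = 66.7% of the set.

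**Conclusion.** The point holds for both run-in rows. The Target Dose Analysis Set is selected on the outcome and cannot serve as a sensitivity set for MRD positivity or conversion before treatment. Two quantities are fixed at 100% regardless of the data: ever-positive status, and conversion among members negative at screening. The contrast of 100% with 33% applies to ever-positive status only. The remaining summaries are not fixed, but they describe treated MRD-positive subjects and not the enrolled population. Separately, the sets named for the final analysis conflict.

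This rests on three assumptions: no subject is treated without a positive MRD result; the approximate planning numbers of 90 and 30 are used for scale; and k, which is not stated, is shown over its full range. The 100% figures depend only on the first.

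The consequence is small. Only exploratory, descriptive endpoints are touched. Nothing here supports an inference that the primary endpoint, its analysis set or the sample size is affected.

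**What to change.** 1. In the last two rows of SAP Table 9-3, replace the sensitivity entry with 'Not applicable'.
2. State in SAP 9.5.3 that these two endpoints use the Pre-treatment Analysis Set at both the primary and the final analysis.
3. Add that exception to the sentence under Table 9-3 and to SAP 7.4, including its general statement on sensitivity analysis.
4. Align Protocol 10.3.4 in the same way. Until the protocol is next amended, record the clarification in SAP Section 10, which now states that there are no changes.

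If timing of positivity among treated subjects is of interest, report it as a description of the treated group. SAP 4.1 already lists the timing category as a covariate.

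The cost is two table cells and a few sentences. One analysis is dropped, and no data collection or sample size changes.
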